Because most SCA occur in unmonitored situations, the nature of arrhythmias that precede and predict SCA in HD patients is uncertain. Evidence from a few continuous monitoring studies suggest that a broad spectrum of arrhythmias is responsible. An analysis of 75 SCA survivors on HD who were subsequently prescribed wearable defibrillators found that ventricular fibrillation (VF) or ventricular tachycardia (VT) were the primary arrhythmia in the majority of recurrent SCA events (79%), whereas only 21% were due to asystole. In contrast, another study that used an implantable loop recorder (ILR) to monitor 50 HD patients found that all 6 SCA events that occurred were preceded by bradycardia/asystole. Furthermore, bradyarrhythmias were the most frequent significant arrhythmias (65%), whereas non-sustained VT was infrequent and detected in only 20%, and there were no episodes of sustained VT. This predominance of bradyarrhythmias echoes observations in the Monitoring in Dialysis study (MiD) in which ILR were implanted in 66 HD patients followed for 6-12 months. Two-thirds of all subjects experienced a serious arrhythmia. The majority were

ILM-detected arrhythmias	Number of detected events	Patient Prevalence
Overall detected serious arrhythmia events	1700	66.7% (44/66)
Sustained VT $\geq$ 30 sec	1	1.5% (1/66)
Bradycardia $\leq$ 40 BPM x $\geq$ 6 seconds	1481	19.7% (13/66)
Asystole $\geq$ 3 sec	14	9.1% (6/66)
Patient marked event with reviewer confirmed arrhythmia	198	57.6% (38/66)
Atrial Fibrillation	4464	40.9% (27/66)

**Table 1:** Arrhythmias in MiD

bradycardia or asystole whereas sustained VT was detected in only 1 patient. (**Table 1**).

In summary, both non-ventricular arrhythmias (bradycardia /asystole) and ventricular arrhythmias (VT) are potentially important causes of SCA in HD patients. They occur frequently with a sufficiently high incidence to serve as endpoints in interventional trials, and the current trial design leverages ILR technology to comprehensively capture all significant arrhythmias that are reasonable surrogates of SCA risk.

[figure not shown]

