## **VI. Biostatistical Analysis**

Given an overarching aim to assess definitive trial feasibility, analyses will be considered exploratory and conservatively interpreted but no adjustment will be made for multiple comparisons.

**Trial Endpoints and Overview of Specific Aims:** The long-term goals are to conduct well-powered trials testing the effect of POC testing-guided management of dialysate potassium and bicarbonate or limitation of maximum UF rate on clinically significant arrhythmia (CSA) and hard cardiovascular events. The specific goals of Studies A/B in accordance with the R34 funding mechanism isto provide the key feasibility and effect-size data necessary to plan definitive, subsequent multi-center trials. Towards this end, data on:

- Aim 1: Adherence with Proposed Interventions
- Aim 2: Recruitment Feasibility
- Aim 3: Effect Estimates

**Adherence with Proposed Interventions (Aim 1)**— In routine practice, the dialysis prescription is adjusted by the physician only once per month in response to monthly laboratory results. Utilizing POC testing and daily adjustment of the dialysate prescription deviates from this standard considerably. Similarly, while a post-dialysis target weight is prescribed by dialysis providers, in routine practice, patients and nurses have daily discretion regarding UF rate. In short, protocolizing the interventions represent a significant change from standard of care that will require active engagement of both patients and HD-unit staff. Estimating the extent of protocol deviation and the safety of proposed interventions in this environment is critical to large-scale implementation of the proposed trials as biologic efficacy is immaterial if interventions cannot be scaled-up.

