**Safety Endpoints**—The primary safety endpoint will include the incidence of all serious adverse events and intervention-specific complications: a) Potassium Intervention—severe K abnormalities ( $K \geq 6.5$  or  $\leq 3.0$  mEq/L), or unscheduled HD or hospitalization for hyper/hypokalemia in the absence of a missed treatment; b) Bicarbonate Intervention—severe  $HCO_3$  abnormalities ( $HCO_3 < 20$  or  $> 32$  mEq/L) or unscheduled HD or hospitalization for acid base abnormalities in the absence of a missed treatment; c) Ultrafiltration Intervention—Unscheduled HD or hospitalization for volume overload. Secondary safety endpoints include the occurrence of CSAs requiring further management, all-cause mortality, cardiovascular mortality, and hospitalization.

**Recruitment Feasibility (Aim 2)**—Recruitment feasibility will be analyzed by testing whether an overall recruitment rate of 1 patient/month is achieved in each trial (1-sample test). This is a critical metric, as a large-scale trial cannot be feasibly completed in a practical number of centers if between 0.5-1 patient/month cannot be enrolled. This rate represents a minimum criterion for feasibility.

The percent of screened patients enrolled will be calculated as a secondary feasibility measure to assess the size of the necessary screening pool. Reasons for non-enrollment (vis-a-vis inclusion and exclusion criteria and patient and physician preferences) will be assessed to determine the potential for protocol modification to improve recruitment. Subject retention will be calculated as the percentage of enrolled patients completing the trial. Retention rates of 90% will be considered the benchmark for feasibility.

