**Effect Estimates (Aim 3)**—Estimating the mean and standard deviation (SD) of the change in duration of clinically significant arrhythmia (CSA) per month is critical for power and sample size calculation and planning definitive studies. The total monthly duration of CSA (in minutes) will be utilized as the primary efficacy endpoint in comparing each pair of interventions (K removal maximization vs. minimization, acidosis vs. alkalosis avoidance, aggressive vs. conservative UF). In the event of incomplete follow-up, CSA duration will be indexed to follow-up time. CSA will be defined on the basis of arrhythmias likely to lead to SCA or serious morbidity and mortality and will include AF, asystole  $\geq 3$  seconds, bradycardia  $\leq 40$  beats per minute lasting  $\geq 6$  seconds, and sustained VT  $\geq 130$  beats per minute lasting  $\geq 30$  seconds. CSA's will be adjudicated by study electrophysiologists.. Currently, no data exists on the expected impact of the interventions on CSA duration, but given a mean duration of CSA in MiD of  $356 \pm 1765$  minutes, a sample size of 20 subjects provides 80% power for detection of change in CSA duration of 140 minutes/month given within-subject correlation of 0.9, 370 minutes for within-subject correlation of 0.7, and 470 minutes if within-subject correlation is 0.5.

**Statistics and Analysis**—A balanced, uniform crossover design will be used with randomization stratified by site in blocks of 4.

**Adherence** will be estimated as % (95% CI) of sessions without protocol deviation. Comparison of adherence percentage pre- vs. post-interim analysis of adherence will be made using linear regression with time period as an independent variable. Exploratory analyses will assess association of adherence with site, dialysis shift (1st-3rd), and day (Monday/Wednesday/Friday or Tuesday/Thursday/Saturday).

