**Safety** will be assessed by calculating the incidence rate (complications per unit follow-up time) for serious adverse events and intervention-specific complications. Comparisons of incidence rate between interventions will utilize Poisson regression adjusted for randomization scheme and site. Exploratory analyses will assess age, sex, race, mean intra-dialytic weight gain, potassium concentration and HCO3 concentration in month prior to randomization on the incidence of adverse events. Given the pilot nature of the trials and major goal of informing feasibility estimates for definitive trials, P<0.05 will be considered significant in all safety analyses. No adjustments will be made for multiple comparisons given the pilot nature of the studies.

**Efficacy** estimates for Aim 3 will utilize the mean duration of CSA as the primary outcome. In the event of incomplete follow-up, this will be indexed to duration of follow-up time (e.g. minutes per day). Change in CSA duration between interventions will be analyzed using mixed effects linear regression with terms for treatment, research site, period, sequence, and random effects for subjects. Primary outcomes for the dialysate trial will compare CSA during potassium maximization vs. minimization, and acidosis vs. alkalosis avoidance. For the UF trial, aggressive vs. conservative UF will be compared. Physiologically, the washout period of 1-week in the dialysate trial and 1 weekend in the UF trial is sufficient to avoid the possibility of carryover effects. Potential for sequence effects is minimized by a design with uniform sequences (all treatments appear once within each sequence). Potential for carryover and randomization sequence effects will be analyzed by including terms for sequence and their interaction with treatment in the models.

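### The 140-minute detectable change at correlation 0.9 does not fit the 370 and 470 minutes beside it: on their SD it would be about 210-214 minutes, and power at 140 about 45%, not 80%

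*Combined protocol and SAP*

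**What the plan says.** Section VI, Effect Estimates (Aim 3), makes total monthly duration of clinically significant arrhythmia (CSA) the primary efficacy endpoint. It says that estimating the mean and SD of its change "is critical for power and sample size calculation and planning definitive studies". From a CSA duration of 356 ± 1765 minutes in the earlier Monitoring in Dialysis (MiD) study, it states that 20 subjects give "80% power for detection of change in CSA duration of 140 minutes/month given within-subject correlation of 0.9". For the two lower correlations the same sentence lists these detectable changes: "370 minutes for within-subject correlation of 0.7, and 470 minutes if within-subject correlation is 0.5".

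The planned efficacy analysis (Section VI, Statistics and Analysis) is "mixed effects linear regression with terms for treatment, research site, period, sequence, and random effects for subjects".

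Three inputs to the power statement are not given:

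- **Time basis of 356 ± 1765.** Section I describes MiD as a study "in which ILR were implanted in 66 HD patients followed for 6-12 months", so the figure could be monthly or cover the whole follow-up.
- **Alpha for efficacy.** The only significance level in the section is for safety: "P<0.05 will be considered significant in all safety analyses".
- **Method of calculation.** None is named.

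**The concern.** One SD, one sample size and one power are given, and only the correlation changes between the three figures. The detectable change should then follow a fixed pattern. The step from 140 to 370 looks far too large for a move from correlation 0.9 to 0.7, while the step from 370 to 470 looks about right.

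This is the protocol's only quantified power statement, and the entry that does not fit is the most favourable one. A reader would take from it that 20 subjects can reliably detect a change of 140 minutes a month if months within a subject are highly correlated. If that is wrong, the expected precision of Aim 3 is overstated.

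**Working it through.** **Inputs.** From Section VI: n = 20, power 80%, SD 1765, correlations (rho) 0.9, 0.7 and 0.5, stated changes 140, 370 and 470. Assumed because not stated: two-sided alpha 0.05 and a paired t calculation, which is the simple counterpart of the planned linear mixed model.

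**Formula.** SD of the within-subject difference = SD × √(2(1 − rho)). The multiplier √(2(1 − rho)) is 0.4472, 0.7746 and 1 at the three correlations. By the noncentral t with 19 df, the detectable difference is 0.6604 SDs of the difference.

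**1. Trying to reproduce the plan's figures from the printed SD (read as monthly, normal differences).**

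| rho | Stated | 0.6604 × multiplier × 1765 | Power at stated value |
|---|---|---|---|
| 0.9 | 140 | 521 | 12% |
| 0.7 | 370 | 903 | 21% |
| 0.5 | 470 | 1166 | 20% |

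None reproduces.

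**2. Ratios.** In the ratio of two detectable changes, SD, n, alpha and power cancel, leaving √((1 − rho₁)/(1 − rho₂)). This check needs none of the unstated inputs.

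| Pair | Required | Stated | Range if rounded to nearest 10 |
|---|---|---|---|
| 0.7 against 0.9 | √3 = 1.73 | 370/140 = 2.64 | 2.52-2.78 |
| 0.5 against 0.9 | √5 = 2.24 | 470/140 = 3.36 | 3.21-3.52 |
| 0.5 against 0.7 | √(5/3) = 1.29 | 470/370 = 1.27 | – |

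Both ratios that involve 140 fail. The one without it fits.

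**3. SD implied by each figure.**

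- 140/(0.6604 × 0.4472) = 474
- 370/(0.6604 × 0.7746) = 723
- 470/(0.6604 × 1) = 712

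One-sided 0.05 gives 543, 828 and 815, the same mismatch.

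**4. The entry at 0.9 on the shared SD.** 370/1.732 = 213.6 and 470/2.236 = 210.2, so about 210-214 minutes.

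**5. Consequences with SD about 720 (inferred, not printed).**

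| rho | Detectable change, n = 20 | Power at stated value | 95% CI half-width | Detectable change, n = 18 |
|---|---|---|---|---|
| 0.9 | 213 | 46% | 151 | 226 |
| 0.7 | 368 | 80% | 261 | 391 |
| 0.5 | 476 | 79% | 337 | 505 |

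The half-width is t(0.975, 19) × SD of the difference/√20. Power at 140 is 46.3% for SD 712 and 45.2% for SD 723; one-sided 0.05 would give 49-50%. Reaching 80% at 140 takes 43 pairs (SD 712) to 44 (SD 723). The n = 18 column is the plan's own retention target ("Retention rates of 90% will be considered the benchmark for feasibility"), where power at 140 falls to about 41%. A two-sequence crossover with 18 df gives 213, 370 and 477, so the paired approximation is not the cause.

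**6. Skewness.** An SD five times the mean implies very skewed durations. I simulated an assumed lognormal model with monthly mean 356 and SD 1765, an additive shift and a paired t-test. It gives detectable changes of about 198, 354 and 476 minutes, and power at the stated values of 70%, 81% and 80%. This roughly recovers 370 and 470 from the printed SD, but not 140. Power at 140 is 69% with 18 pairs and still only about 77% with 50. Two other assumed skewed models gave less at 140: 49% (lognormal, correlation on the log scale) and 34% (gamma with a normal copula).

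**The case against.** Five points can be made for the plan.

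- **The 45% rests on an SD the protocol never states.** True. About 720 is back-solved from 370 and 470. On the printed 1765 with normal differences all three entries fail, and 140 is not special. The ratio mismatch does not depend on any SD.
- **The lognormal reading uses the printed mean and SD, and gives 70% rather than 45%.** Fair, and it may be closer to what was done. It still puts the entry at 0.9 near 198 minutes.
- **Another test could reach 80%.** In the same lognormal model a Wilcoxon signed-rank test has about 97% power at 140. So no claim can be made that every method falls short. But that test is not the planned linear model, and it gives about 98% at 370 and 470, so it does not produce the three stated figures either.
- **The slip may be elsewhere.** Keeping the SD implied by 370 and 470, 140 minutes would fit a correlation of about 0.956. Two entries agreeing against one is suggestive, not proof. This is a reason to recompute all three rather than edit one number.
- **It is a pilot.** Section VI says "analyses will be considered exploratory and conservatively interpreted", Section IX sets no formal stopping rules, and definitive studies are to be planned from the pilot's own mean and SD. This stands and limits the consequence.

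**Conclusion.** The concern holds. Under a standard paired calculation the three figures cannot all come from one SD, whatever the alpha, sample size or power, and 140 is the one out of line.

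On the SD that fits the other two entries, with two-sided 0.05 assumed, the entry at 0.9 should be about 210-214 minutes and power at 140 is about 45%. Over the t-test and normal-theory readings tried, power at 140 runs from 12% (printed SD, normal differences) to 70% (assumed lognormal), and none reaches 80%. Which reading the authors intended cannot be recovered from the text.

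The effect is confined to the stated precision of Aim 3. It should be fixed, but it does not undermine the pilot's design.

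**What to change.** In Section VI, Effect Estimates (Aim 3), recompute all three detectable changes from one stated monthly SD. State that SD's time basis, the alpha and its sidedness, and the method. Replacing 140 alone would make the figures agree with each other but not with the printed 1765.

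For orientation, under normal theory with n = 20 and two-sided 0.05:

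- **SD about 720:** detectable changes of about 213, 368 and 476 minutes; 95% CI half-widths of about 151, 261 and 337.
- **SD 1765:** detectable changes of about 521, 903 and 1166 minutes; half-widths of about 369, 640 and 826.

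The 720 is inferred and should be printed only if the authors can source it. Alternatively, report a simulation that allows for skewness, with its model stated. Either way, give the half-widths for the same SD and say that the normal-theory figures assume normal differences.

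The cost is one paragraph of text and a less favourable stated figure. No patients, visits or analyses are added.

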## Study Summary

[figure not shown]
Title	Reducing Arrhythmia in Dialysis by Adjusting the Rx Electrolytes/Ultrafiltration
Short Title	RADAR
Protocol Number	
Phase	Pilot
Methodology	
Randomized, Crossover, Blinded, Multi-arm
 
Interventions:
 
Implanted Loop Recorder
 
Potassium/Bicarbonate Trial (Study A)
 
Ultrafiltration Trial (Study B)

Study Duration	24 months
Study Center(s)	
Duke University Medical Center (DUMC)
 
New York University Langone Health (NYU)-coordinating site receiving funding from the NIH with dialysis unit located at Lower Manhattan Dialysis Center ([name]).

Objectives	
 
• To obtain pilot data on adherence, safety and barriers to implementation of proposed interventions.
 
• To obtain pilot data on recruitment feasibility and subject retention.
 
• To obtain pilot data to estimate the potential effect sizes of proposed interventions.
 

Number of Participants	
40 (20 in each of two interventions)
 
(60 participants enrolled with 40 expected to reach randomization. Because patients have the option of enrolling in both study A and B it is possible that the total number of devices required will be less than 40.)

Diagnosis and Main Inclusion Criteria	Dialysis-dependent end-stage renal disease
Study Product/Intervention, Route, Regimen	
Study A: Potassium/Bicarbonate Four-Arm Crossover
 
Potassium (K) Removal Maximization strategy, 1 month (lower dialysate K)
 
Potassium (K) Gradient-Minimization Strategy, 1 month (higher dialysate K)
 
Acidosis Avoidance, 1 month (higher dialysate bicarbonate)
 
Alkalosis Avoidance, 1 month (lower dialysate bicarbonate)
 
Study B: Dialysis Ultrafiltration Rate (UFR) Two-Arm Crossover
 
UFR <math>\leq</math>10 ml/kg/hr, 1 month
 
UFR as needed, 1 month

Ancillary Products:	
LINQ™ (Medtronic) Implantable Cardiac Loop Recorder (Carelink System)
 
i-STAT (Abbott)- Study A only

Duration of administration	LINQ™: 3-6 months Study A: 4 months Study B: 2 months

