## II. Specific Aims

Overview of Trial Design—The overall goal for these trials is to provide the data necessary for the design of definitive clinical trials. Specifically, we aim to test recruitment feasibility, the feasibility of POC electrolyte measurement and POC-directed management of the dialysis prescription, and to provide preliminary estimates of effect size with manipulation of UF rate, dialysate K, and dialysate HCO3. We will perform two related, randomized cross-over trials; Study A- dialysate interventions trial, consisting of 2 dialysate potassium interventions and 2 dialysate bicarbonate interventions (4 total cross-over interventions); and Study B-ultrafiltration rate intervention trial, consisting of 2 separate ultrafiltration rate strategies.

The central hypothesis underlying Study A and Study B is that the risk of clinically significant arrhythmias in HD patients can be reduced by altering components of the dialysis prescription.

**Aim 1—To test the feasibility and safety of POC-guided dialysate prescription adjustment and the feasibility of limiting UF rate in HD patients.** The current studies will pilot our educational strategies and the dialysate potassium, dialysate bicarbonate and UF intervention strategies to test their feasibility in a multi-center setting. They will test the hypothesis that  $\geq 80\%$  adherence with proposed interventions is feasible, and that the safety need for unscheduled dialysis or severe abnormalities in potassium and bicarbonate will be minimal.

**Aim 2—To assess recruitment feasibility and retention rate for trials combining ILR insertion to monitor arrhythmia and interventions using POC-guided dialysis prescription or UF rate manipulation.** Screen failures and retention rates will be captured and analyzed. Whether recruitment rates  $\geq 1$  patient per month and retention rate  $> 90\%$  are achievable in each study will be tested.

**Aim 3—To refine effect estimates of the change in monthly CSA duration during Study A (dialysate potassium intervention to maximize vs. minimize intradialytic potassium removal) and Study B (aggressive vs. conservative ultrafiltration rate).** Refining estimates of change in CSA with each pair of interventions will provide key information necessary for design of definitive trials. Whether CSA decreases with minimization of potassium removal, alkalosis limitation and UF rate minimization will be tested.

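### The Aim 3 power sentence does not follow from its own SD: recomputed, the 80%-power changes are about 521, 903 and 1166 min/month, all above the 356-minute planning mean

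*Combined protocol and SAP*

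**What the plan says.** Section VI (Biostatistical Analysis, Effect Estimates for Aim 3) sets the endpoint: "The total monthly duration of CSA (in minutes) will be utilized as the primary efficacy endpoint". It takes a mean of 356 with SD 1765 minutes from the earlier loop-recorder cohort in dialysis patients (MiD) and concludes that "a sample size of 20 subjects provides 80% power for detection of change in CSA duration of 140 minutes/month given within-subject correlation of 0.9", then "370 minutes for within-subject correlation of 0.7, and 470 minutes if within-subject correlation is 0.5". No time unit is attached to 356, and no mean is given for either strategy in any contrast. The same paragraph concedes: "Currently, no data exists on the expected impact of the interventions on CSA duration".

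The analysis is within subject: "Change in CSA duration between interventions will be analyzed using mixed effects linear regression with terms for treatment, research site, period, sequence", with random subject effects. No alpha or sidedness is given for efficacy. The only stated threshold concerns safety: "P<0.05 will be considered significant in all safety analyses".

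The purpose is described in two ways. The Study Summary lists as an objective "To obtain pilot data to estimate the potential effect sizes of proposed interventions". Aim 3 in Section II adds a directional test: "Whether CSA decreases with minimization of potassium removal, alkalosis limitation and UF rate minimization will be tested".

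**The concern.** CSA minutes cannot be negative, so a mean reduction cannot exceed the mean it starts from. Two of the three changes said to be detectable already lie above the only mean in the plan, and the plan never makes that comparison. The power sentence therefore describes sensitivity to reductions that cannot occur from that mean, beside an aim that says a decrease will be tested.

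The three figures are also too small for an SD of 1765 and 20 subjects, so the design is less sensitive than printed. A reader planning the definitive trial would take from this sentence a wrong idea of how much the pilot's mean change can be trusted.

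**Working it through.** **Inputs.** Mean 356, SD 1765, n = 20, power 80%, correlations 0.9, 0.7 and 0.5, and stated changes 140, 370 and 470 are all from Section VI. Two-sided alpha of 0.05 is my assumption. The 20 subjects are taken as complete.

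**1. Printed figures against the printed mean.** 140/356 = 39%; 370/356 = 104%; 470/356 = 132%. The excess at correlation 0.7 is only 14 minutes.

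**2. Can the printed figures be reproduced?** For a paired comparison, SD of change = SD × √(2(1 − ρ)). The detectable change is that value times a constant fixed by n, alpha and power.

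- At 80% power, two-sided 0.05 and n = 20, the paired t constant is 0.660.
- The normal approximation constant is (1.960 + 0.842)/√20 = 0.626.

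| ρ | SD of change | Detectable, paired t | Detectable, normal | Printed | Paired t as % of 356 |
|---|---|---|---|---|---|
| 0.9 | 789 | 521 | 494 | 140 | 146% |
| 0.7 | 1367 | 903 | 856 | 370 | 254% |
| 0.5 | 1765 | 1166 | 1106 | 470 | 327% |

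The printed figures are not reproduced. Looser error rates do not help: the paired t values are 455, 789 and 1018 at one-sided 0.05, and 383, 664 and 857 at one-sided 0.10. All still exceed 356. Other forms of the SD of change, larger n and a parallel-group layout also failed to return 140/370/470.

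**3. Could one different SD explain them?** With a common SD, n and alpha, the figures must stand in the ratio of √(1 − ρ).

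- 0.7 against 0.5: √(0.3/0.5) = 0.775; printed 370/470 = 0.787. This is close.
- 0.9 against 0.5: √(0.1/0.5) = 0.447; printed 140/470 = 0.298. This does not fit; 470 would imply about 470 × 0.447 = 210.

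No single SD gives all three, so 140 is out of line even with its neighbours.

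**4. Power at the printed changes, with SD 1765** (noncentral t, 19 df): about 12% for 140 at 0.9, 21% for 370 at 0.7 and 20% for 470 at 0.5.

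**5. Is any reduction from 356 powered?** The required ratio of mean change to SD of change is 0.660. With equal SDs in both periods, the ceiling of 356 gives 356/789 = 0.451, 356/1367 = 0.260 and 356/1765 = 0.202.

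Equal SDs are unlikely for a large reduction of a non-negative quantity, so let the mean and SD both shrink by a fraction p. The ratio is then (356/1765) × p/√(p² + 2(1 − p)(1 − ρ)). This cannot exceed 356/1765 = 0.202, because the added term under the root is never negative. Neither version reaches 0.660.

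**6. Expected precision.** 95% CI half-width = 2.093 × SD of change/√20, which is about 369, 640 and 826 minutes at correlations 0.9, 0.7 and 0.5.

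**The case against.** **The mean is not a comparator mean.** It comes from an observational cohort followed for 6–12 months, with no time unit, and each contrast is between two active strategies. Section I itself says that either potassium approach might provoke arrhythmia. A difference above 356 is therefore possible if one strategy raises CSA above that level. This stands. A reader might infer that no possible difference is powered, or that calling the strategies standard care makes a large difference implausible. The documents support neither. The conclusion must stay conditional and be limited to reductions from 356.

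**The printed excess at 0.7 is trivial.** It is 4%, on a figure that looks rounded to tens. This also stands. On the printed figures alone only the 0.5 case is clearly beyond the mean, so the point rests mainly on the recomputation. Equally, a reader should not infer that the 0.9 case is sound because 140 lies below 356; that figure is the least supported of the three.

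**Power for complete abolition of CSA.** It is tempting to quote this at each correlation. It should not be done: if every treated value is zero, the within-subject correlation is undefined and the SD of change is simply the single-period SD. SDs back-solved from 370 and 470 should not be used either, since the document does not state them.

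**This is an exploratory pilot.** Section VI calls for conservative interpretation, and Aim 3 is headed as refining estimates. Nothing in the plan says that a null result will be read as no effect, and I do not claim that. The pilot status limits the consequence, but it does not make the power sentence correct.

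**Conclusion.** The power sentence is wrong as printed and conceals how little the pilot can detect. On the plan's SD and sample size, the 80%-power changes are about 521, 903 and 1166 min/month, not 140, 370 and 470, and all exceed the 356-minute planning mean. If 356 is the monthly mean under the comparator strategy, no reduction from it reaches 80% power at any of the three listed correlations.

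This rests on two-sided 0.05, 20 complete subjects, a paired t analysis standing in for the mixed model, and 356 and 1765 being monthly figures. The t calculation is approximate for a non-negative variable whose SD is about five times its mean (1765/356 = 4.96). The normal approximation and one-sided alphas up to 0.10 leave all three changes above 356.

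**What to change.** In Section VI, Effect Estimates (Aim 3):

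- Replace 140/370/470 with about 521/903/1166 min/month, or state the different SD actually used and its source. In the second case 140 must still be brought into line with the other two.
- State the alpha and sidedness for efficacy, and the time unit of 356 and 1765.
- Say plainly that these changes exceed the planning mean.
- Replace the power claim with expected precision: 95% CI half-widths of about 369, 640 and 826 minutes at correlations 0.9, 0.7 and 0.5.

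In Section II, present Aim 3 as estimation of the mean and SD of change and the within-subject correlation, with confidence intervals, in place of the statement that a decrease will be tested. This agrees with the Study Summary objective.

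The cost is wording only. Sample size, procedures and data collection are unchanged. The stated sensitivity becomes less favourable.
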